5.2.4 Termination criteria for the study in general

The clinical study can be terminated by the coordinating investigator if new findings and/or risks should come to light that necessitate a reassessment of the risk/benefit ratio and which results in a negative result.

5.2.5 Definition of the end of the study

The study is completed when all patients have either died or been followed up for at least 6 months, or the study has been terminated.

The patient will continue to receive treatment at the clinic in question after the 6-month follow-up period, or the premature termination of the study for the patient.

6 Treatment

6.1 Patient registration

The patients were assigned 2 code numbers, the number of the contributing center plus a patient ID number starting with 001 and chronologically ongoing.

Coordination and supervision of the inclusion of the patients will be performed by the Department of Radiation Oncology of the University of Lübeck, Germany.

Patients can be registered by e-mail ([contact]) or by [contact]).

6.2 Treatment

6.2.1 Radiotherapy

Radiotherapy is administered as high-precision radiotherapy with 25.0 Gy in 1 week, i.e. with 5.0 Gy per fraction on 5 days per week (representing an EQD2 of 43.8 Gy for radiation myelopathy) [6, 7]. An EQD2 of 45 Gy is estimated to be associated with a risk of radiation-related myelopathy of 0.03% and is therefore considered safe [8]. VMAT (6-10 MeV photon beams) is the preferred technique. SBRT is allowed for patients with involvement of only one vertebra, if the following constraints can be met. The clinical target volume (CTV) includes the vertebral and soft tissue tumor as seen on the planning computed tomography and diagnostic MR-imaging, the spinal canal, the width of the involved vertebrae, and half a vertebra above and below those vertebrae involved by MSCC. The planning target volume (PTV) should include the CTV plus 0.8 cm and should be covered by the 95%-isodose. The maximum relative dose allowed to the spinal cord is 101.5% of the prescribed dose (representing an EQD2 of 44.9 Gy for radiation myelopathy). This maximum dose is estimated to be associated with a risk of radiation-related of <0.03% and is, therefore, also considered safe [8]. Both the EQD2 of the prescribed dose (41.7 Gy) and the EQD2 of the maximum dose (43.8 Gy) are well below the tolerance dose of bone [9-11]. In accordance with the Quantitative Analyses of Normal Tissue Effects in the Clinic (QUANTEC) data, the mean doses (EQD2) for esophagus, heart and lung must be <34 Gy, <26 Gy and ≤ 7 Gy, respectively [9]. Taking into account a radiation regimen of five fractions, the corresponding mean doses per fraction are 4.5 Gy, 3.8 Gy and 1.54 Gy, respectively [6, 7]. MSCC may affect single or multiple spinal sites. All sites need to be treated with high-precision RT following the dose prescriptions and constraints given above.

6.2.2. Concomitant treatment

It is recommended that the patients receive concomitant dexamethasone during the period of radiotherapy if indicated [1, 2]. [Regarding dose, type and duration of treatment, contraindications, side effects, pharmacological characteristics and pharmaceutical details about dexamethasone, please see relevant product information in the patient information leaflet included in the drug package.]

6.2.3. Possible side effects of high-precision RT

High-precision RT in the thoracic spinal area may be associated with nausea and vomiting, whereas RT in the lumbar spine may be associated with diarrhea. In case of grade 3 toxicity according to Common Terminology Criteria for Adverse Events (CTCAE), RT may be delayed for a maximum of 7 days. If the symptoms persist, RT will be terminated. If RT has to be terminated, the head of the clinical study has to be informed.

7 Safety Management

7.1 Definitions

7.1.1 Adverse events

An adverse event (AE) is any event experienced by a patient or subject of a clinical study, which does not necessarily have a causal relationship to treatment. An AE can therefore be any adverse or inadvertent occurrence (including notable laboratory findings), symptom or illness that occurs in the treatment period, no matter whether there is a causal relationship or not. Existing illnesses that deteriorate during the study should be reported as AE. They may lead to SAEs if they fulfil the criteria below.

Events covered by the documentation for concomitant diseases, the skin status or the radiation related acute toxicity grade (CTCAE v4.03) Grade 1 do not have to be additionally documented as adverse events. If an additional concomitant disease appears after the start of the study an adverse event form has to be completed.

7.1.2 Unexpected adverse events

Unexpected adverse events (UAEs) are those whose type, frequency and degree of severity are not expected based on current knowledge.

7.1.3. Serious adverse events

Serious adverse events (SAEs) are those which fulfil one of the following criteria at any dose level:

- Lethal (resulting in death) event (Note: death is the result, not the event itself)
- Life-threatening event (Note: the term “life-threatening” refers to an event in which the patient was in danger of death at the time the event occurred but not to an event that may have resulted in death had it been more serious.)
- Patient had to be admitted to hospital or his/her hospital stay had to be extended as a result of the event
- Any event leading to permanent or significant disability.
- Birth defects or malformations
- Any medically significant intervention in order to prevent one of the outcomes mentioned above

Hospitalization should be defined as such that the hospitalization was necessary in order to treat the AE. Hospital stay as part of the treatment outlined in the protocol or as a result of a planned, elective operation is not classified as SAE. Likewise, an elective hospitalization to facilitate the study process does not count as SAE.

7.2 Assessment and documentation of adverse events

The severity of AEs should be assessed for clinical effects according to the following scale:

1 = mild, 2 = moderate, 3 = severe, 4 = life-threatening and 5 = fatal.

The following scale should be used to describe the likelihood that the event was caused by the study treatment: **1 = certain/definitely caused by study treatment; 2 = probable; 3 = possible; 4 = unlikely; 5 = not related; and 9 = not assessable.**

7.3 Reporting of adverse events

SAEs and UAEs must be reported within 24 hours after their detection/onset by fax to the address below (see separate document attached to the case report form):

[name]. [name]

*Klinik für Strahlentherapie, Universität zu Lübeck
[name]*

[contact]

[contact]

Email: [contact]

8 Assessments

8.1 Summary of assessments

The following assessments will be performed as part of this study:

	Prior to RT	End of RT	Follow up at 1 month (+/- 2 weeks) following RT	Follow up at 3 months (+/- 2 weeks) following RT	Follow up at 6 months (+/- 2 weeks) following RT
Informed Consent	X				
Medical History/Concomitant Diseases	X				
Prognostic factors	X				
Physical examination	X	X	X	X	X
Inclusion/Exclusion Criteria	X				
Motor Function	X	X	X	X	X
Sensory Function	X	X	X	X	X
Sphincter Dysfunction	X	X	X	X	X
Ambulatory Status	X	X	X	X	X
Pain	X	X	X	X	X
Distress (quality of life)	X	X	X	X	X
Toxicity*	X	X	X	X	X
LPFS		X*	X	X	X
Overall Survival		X*	X	X	X

*also during RT

8.2 Data assessment and prior to start of high-precision RT

The following parameters will be recorded at the start of the study:

Date of birth (age), gender, time between onset of motor deficits and start of RT, type of imaging used for diagnosis of MSCC, interval between initial tumor diagnosis and MSCC, dexamethasone treatment, surgical consultation, localization and number of involved vertebrae, type of primary tumor / histology, presence of other bone metastases or visceral metastases prior to RT, performance status (ECOG-PS, **Appendix IV**), motor function / ambulatory status (according to the modified Tomita scale [17], sensory function, sphincter dysfunction, pain score, and distress (as an indicator of quality of life) score [18] (**Appendix III**).

8.3 Assessments with respect to primary and secondary endpoints

The following parameters will be assessed continuously throughout the course of the study:

8.3.1 Local progression-free survival

Local progression-free survival (LPFS) is defined as freedom from progression of motor deficits during RT and freedom from an in-field recurrence of MSCC (i.e. freedom from motor deficits due to a recurrence of MSCC in the previously irradiated parts of the spine) following RT [5]. LPFS time will be calculated from the last day of the radiotherapy treatment. LPFS will be regularly assessed clinically (physical examination) at 1, 3 and 6 months following RT. In case of a suspected recurrence of MSCC (i.e. progression of existing or development of new motor deficits), a spinal MR-imaging will be performed to confirm or exclude an in-field recurrence of MSCC. In case of progression of existing or development of new motor deficits between two regular follow-up visits, spinal MR-imaging will be performed at any time. The number of MR-imaging sessions is minimized to clinically relevant situations, since patients with MSCC are often quite debilitated. Thus, diagnostic procedures, which may be burdensome for the patients, may not be performed for study purposes alone. The medical history/concomitant diseases will be assessed once at baseline. Newly developed diseases have to be documented as adverse events.

8.3.2 Motor function / Ability to walk

Motor function will be evaluated using the following scale according to Tomita et al. [17] prior to RT, at the end of RT, and at 1, 3 and 6 months following RT. Improvement or deterioration of motor function was defined as a change of at least 1 point.

- 0 = Normal strength
- 1 = Ambulatory without aid
- 2 = Ambulatory with aid
- 3 = Not ambulatory
- 4 = Complete paraplegia

Motor function will additionally be evaluated separately for each leg using the following scale in reference to the American Spinal Injury Association (ASIA) classification [19] resulting in total points of 0 to 14. Improvement or deterioration of motor function was defined as a change of at least two points.

- 0 = Complete paraplegia
- 1 = Palpable or visible muscle contractions
- 2 = Active movement, without gravity
- 3 = Active movement, against gravity
- 4 = Active movement, against mild resistance
- 5 = Active movement, against intermediate resistance
- 6 = Active movement, against strong resistance
- 7 = Normal strength

8.3.3 Sensory function / Sphincter dysfunction

Sensory function:

Sensory function will be evaluated using the following scale, modified in accordance to the ASIA classification [19].

0 = Absent

1 = Impaired

2 = Normal

9 = Cannot be assessed

Sphincter dysfunction:

Sphincter dysfunction will be evaluated as yes vs. no.

8.3.4 Overall survival

Overall survival (OS) time will be calculated for each patient from the last day of radiotherapy up to 6 months following RT. Patients will be followed up until death or for at least 6 months.

8.3.5 Pain

Vertebral pain will be evaluated with a numeric rating scale (self-assessment by patients) from 0 to 10 points (0=no pain, 10=worst pain) prior to RT and directly, 1, 3 and 6 months following RT. Improvement by two points is rated partial response (PR), 0 points complete response (CR). Pain will be assessed prior to RT and directly and 1, 3 and 6 months following RT.

8.3.6 Distress (as an indicator of quality of life)

Distress will be assessed using the distress thermometer (**Appendix III**) [18]. Patients can rate their distress between 0 and 10 (0 = no distress, 10 = extreme distress). Distress will be assessed prior to RT and directly and 1, 3 and 6 months following RT. Improvement of distress was defined as a decrease by at least two points compared to the distress-score prior to RT (baseline).

8.3.7 Toxicity

Toxicity will be assessed according to CTCAE 4.03 during RT, directly after RT and at 1, 3 and 6 months following RT [20]. If radiation myelopathy is suspected (i.e. deterioration according to the modified ASIA scale [19]), spinal MR-imaging will be performed.

9 Comparisons to Historical Control Group

The patients of this study who received high-precision RT with 5x5 Gy for MSCC will be matched to historical control group treated with 5x4 Gy of conventional RT between 2001 and 2016. This data set consists of 680 patients.

The patients of the control group are part of an already existing anonymized database. To be eligible for control group, patients fulfilling the same inclusion criteria and exclusion criteria as defined in the prospective phase II study are considered. Furthermore, to be consistent with efficacy analysis of phase II study, patients of the historical control group must have received at least 80% of the planned RT dose. This will lead to more than 600 patients qualifying for the comparison with the prospectively collected phase 2 data.

For comparison purposes, a propensity score approach will be applied to account for baseline differences between treatment arms to balance covariates and remove bias that may arise due to these confounders. A propensity score is a conditional probability of assignment to a particular treatment given a number of baseline covariates. Except for unmeasured potential confounding factors, patients having the same propensity score but assigned to different treatments will tend to have the same (or nearly the same) distributions on their background covariates and thus are considered to be similar to random assignment of treatments. To estimate the odds of receiving a specific radiotherapy a non-parsimonious multivariable logistic regression model will be estimated. Covariates to be included in the model will be the following ten prognostic factors [16]:

- Age (2 groups, depending on median age)
- Gender
- Type of primary tumor (breast cancer vs. prostate cancer vs. myeloma/lymphoma vs. lung cancer vs. other tumors)
- Interval from tumor diagnosis to MSCC (≤ 15 vs. > 15 months)
- Number of involved vertebrae (1-2 vs. ≥ 3)
- Other bone metastases at the time of RT (no vs. yes)
- Visceral metastases at the time of RT (no vs. yes)
- Time developing motor deficits prior to RT (1-7 days vs. 8-14 days vs. > 14 days)
- Ambulatory status prior to RT (no vs. yes)
- Eastern Cooperative Oncology Group (ECOG) performance score (1-2 vs. 3-4)

Once estimated, adjustment will be accomplished by stratifying the data set on the propensity score, calculating the treatment effect within strata and then pooling the strata-specific treatment effect estimates.

Rosenbaum and Rubin have shown that perfect stratification based on the propensity score will produce strata where the average treatment effect within strata is an unbiased estimate of the true treatment effect [21]. Due to the differences in total sample size between the phase II study and the historical data set, the stratum boundaries will be based on the values of the propensity score for the phase II data alone.

One approach is to use quintiles of the estimated propensity scores to determine the cut-offs for the different strata. The success of propensity score approach will be examined by examining the covariate imbalance between treatment arms before and after adjusting for their propensity quintile. This will be done using a two-way analysis of variance model which includes main effects for propensity score quintile (codes as a class variable with 4 degrees of freedom) and treatment arm. The F-statistic for treatment arm after adjustment for propensity score quintiles will then be compared with the F-statistics for treatment arm prior to adjustment for propensity score quintile to determine whether balance was achieved after stratification based on the propensity score.

PRE-MODE

Furthermore, the propensity score will be evaluated for good calibration as measured by the propensity score predicted and observed proportions of treatment group arms within quintiles of the propensity score. To investigate whether propensity scores removed bias due to differences in covariates between studies and to compare binary study endpoints after stratification of patients by propensity scores Cochran-Mantel-Haenszel tests were performed.

Comparisons between the patients of the phase 2 study and the historical control group will be performed for LPFS, OS, motor function and ambulatory status.

10 Statistics

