- As described in section 8, the confirmatory study aim is to compare the prospectively collected phase II data with a historical, propensity-score matched cohort collected up to the time of data analysis. Assuming for simplicity and conservative power calculation that this comparison could be conducted with a simple Pearson-Chi-Square test using a two-sided significance level of 5% (10%), a power of 79% (86%) is reached, if 40 patients are treated with high-precision RT and roughly 400 patients of the historical control group qualify for Propensity-Score adjusted comparison and assuming that the expected 6-month LPFS are 87% and 67%, respectively. Taking into account that the more sophisticated propensity-score adjusted statistical analysis (see section 8) will increase statistical power, the power for treatment arm comparison reached

PRE-MODE

with 40 eligible patients in the prospective phase 2 part of the study can be assumed to be at least 80%.

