10.2. Statistical analyses

10.2.1 Primary endpoint:

The primary endpoint (LPFS of MSCC) will be evaluated based on the sample size calculations described above. The evaluation will be performed in those patients, who are available for assessment of the primary endpoint and have received at least 80% of the planned RT dose. Due to the open nature of the study, a blind data review is not necessary. The safety population includes all patients who have received at least 1 fraction of high-precision RT.

LPFS is defined as freedom from progression of motor deficits during RT and freedom from an in-field recurrence of MSCC (i.e. freedom from motor deficits due to a recurrence of MSCC in the previously irradiated parts of the spine) following RT [5]. Deterioration of motor deficits during RT will be counted as LPFS of 0 months. Freedom from an in-field recurrence following RT will be referenced from the last day of RT. To investigate clinically important, sustainable effects of precision radiotherapy and avoid over-evaluation of early temporal shifts without any longer term relevance, study design and analysis focuses on binary endpoints evaluated at 6-months rather than time-to-event analyses.

10.2.2 Secondary endpoints:

Secondary endpoints:

An improvement or deterioration of the motor function will be defined as a change of at least 1 point on a 5-point scale [17]. Effect of RT on motor function and post-RT ambulatory rates will be evaluated directly after RT and at 1, 3 and 6 months following RT in those patients who are alive and available for assessment. To investigate whether propensity scores removed bias due to differences in covariates between studies and to compare binary study endpoints after stratification of patients by propensity scores Cochran-Mantel-Haenszel tests were performed. P-values of <0.05 are considered significant.

Overall survival (OS) will be counted from the last day of RT. To investigate clinically important, sustainable effects of precision radiotherapy and avoid over-evaluation of early temporal shifts without any longer term relevance, study design and analysis focuses on binary endpoints evaluated at 6-months rather than time-to-event analyses. The analysis of OS will be conducted in the intent-to-treat population.

Data regarding sensory deficits, sphincter dysfunction, pain, distress and toxicity will only be assessed in the phase 2 study.

11 Ethical and Legal Principles

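### LPFS is tested over propensity strata without ever being modelled on the ten prognostic factors, so the test is conservative and the power gain claimed in 10.1 is unsupported

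*Combined protocol and SAP*

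**What the plan says.** Section 9 fits one covariate model. Its outcome is which radiotherapy the patient received, and its predictors are the ten factors. For the treatment effect, "adjustment will be accomplished by stratifying the data set on the propensity score, calculating the treatment effect within strata", after which the stratum estimates are pooled. Stratum limits are set on the phase 2 patients; quintiles are offered as one option. Balance is checked with F-statistics before and after stratification, but no action is given if imbalance remains. On testing, sections 9 and 10.2.2 both state that "to compare binary study endpoints after stratification of patients by propensity scores Cochran-Mantel-Haenszel tests were performed", and 10.2.2 adds that "P-values of <0.05 are considered significant".

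Neither section 9 nor section 10.2 models LPFS on the ten factors, as main or sensitivity analysis.

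Section 10.1 supposes for planning that "this comparison could be conducted with a simple Pearson-Chi-Square test". The planned group sizes enter as a condition on that calculation: "if 40 patients are treated with high-precision RT and roughly 400 patients of the historical control group qualify". The LPFS rates enter as a second condition, worded as "assuming that the expected 6-month LPFS are 87% and 67%, respectively". Under these inputs the section reports its result as follows: "two-sided significance level of 5% (10%), a power of 79% (86%) is reached". It then argues that "the more sophisticated propensity-score adjusted statistical analysis (see section 8) will increase statistical power", and concludes that power is at least 80%. No calculation is given for that step.

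**The concern.** The factors are called prognostic and are taken from a study of local control, so they should carry information about LPFS. The plan uses them where data are thin (about 40 phase 2 patients for a 14-term propensity model) and not where data are richer (well over 100 expected LPFS failures, mostly in controls).

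Estimating a propensity score from prognostic factors removes chance imbalance in them, so the true variance of the group comparison falls. The CMH variance treats the strata as given and does not reflect that fall. The test therefore rejects less often than its nominal level allows, and the precision gained is not turned into power. At stake are a few points of power for the confirmatory aim, a small residual bias inside strata, and a sentence in 10.1 that carries the plan over the 80% line without support.

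**Working it through.** **Inputs from section 10.1:** 40 vs 400 patients; LPFS 87% vs 67%; two-sided 5% (10%). Section 9 expects more than 600 controls. **Assumed, because the documents do not give it:** R², the share of LPFS variance explained by the ten factors, with matching covariate frequencies and effects.

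**1. The plan's own figure.**
- Pooled rate = (40×0.87 + 400×0.67)/440 = 0.688.
- Null SE = √[0.688×0.312×(1/40+1/400)] = 0.0768.
- Alternative SE = √[0.87×0.13/40 + 0.67×0.33/400] = 0.0581.
- Power at 5% = Φ[(0.20 − 1.96×0.0768)/0.0581] = 80.2%. At 10% (1.645) it is 89.7%.
- Two-sided Fisher exact gives 79.2% and 86.5%, matching both stated figures (79%, 86%). They look like Fisher powers labelled Pearson.
- With 600 controls the Pearson formula gives 81.7%.

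**2. What prognostic information could add.** Multiply both SEs by √(1−R²). Power at 5% is 82.6% for R² 0.05, 84.1% for 0.08, 85.0% for 0.10, 87.3% for 0.15 and 89.6% for 0.20.

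**3. Simulation of the planned test, balanced groups** (40 vs 400, five strata cut on phase 2 patients, 2,500 trials per row, Monte Carlo SE about 0.8 points). The comparator is a logistic score test for group adjusted for the ten factors. Differences were taken before rounding.

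| R² (c-statistic) | Unadjusted | CMH | Ten factors | Difference |
|---|---|---|---|---|
| 0 (0.50) | 81.7% | 79.6% | 81.2% | +1.6 |
| 0.03 (0.60) | 80.8% | 79.9% | 82.2% | +2.4 |
| 0.05 (0.63) | 81.4% | 80.0% | 83.2% | +3.2 |
| 0.095 (0.68) | 80.8% | 80.2% | 84.5% | +4.3 |
| 0.15 (0.73) | 80.4% | 80.0% | 86.0% | +6.0 |

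CMH is no more powerful than the unadjusted test in any row.

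**4. Unbalanced groups, R² 0.095.**
- Case mix differs but is largely unrelated to prognosis: 79.7% to 83.8%, 79.6% to 84.3%, and 76.7% to 82.0%.
- Phase 2 patients have better prognosis: 76.3% to 78.8% (moderate), 72.2% to 71.2% (strong).
- A separate simulation (40 vs 400-600, R² 0.04-0.16) gave about +3 to +5 points with balance or worse phase 2 prognosis (for example 81.8% to 84.7%, 75.4% to 80.6%), and −1 to +1 with better phase 2 prognosis.

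**5. Two-sided error at nominal 5%.** Across both sets, CMH ran at 3.6-4.6% and the adjusted test at 5.0-5.7%. With propensity strata added to the ten factors, one strongly unbalanced cell reached 6.1% (2,000 trials, Monte Carlo SE about 0.5 points).

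**6. Residual bias.** A crude baseline-risk difference of 4.2 points fell to 0.4 after five strata, and 7.9 fell to 0.9. In the separate simulation, 0.3-1.1 points after strata fell to about 0.1-0.25 after standardisation through an LPFS model.

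**7. Feasibility.**
- Terms: eight binary factors (8), tumour type (4), time developing motor deficits (2) = 14. Adding group makes 15; four stratum terms make 19.
- Expected failures: 40×0.13 + 400×0.33 = 137, or 40×0.13 + 600×0.33 = 203, of which about 5 are in the 5x5 Gy group.
- Failures per coefficient with 137: 9.1 (15 terms) or 7.2 (19 terms).
- Propensity model: 40/14 = 2.9 phase 2 patients per term.

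**The case against.** Propensity stratification with CMH is a recognised, pre-specified method. Section 9 plans balance and calibration checks and does not fix the number of strata at five.

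The strata also do capture prognostic information. In a simulation of 40 vs 600 balanced patients (4,000 trials), nominal powers were 82.5% for CMH vs 85.7% for strata plus factors at c 0.68, and 82.3% vs 88.6% at c 0.75. With each test calibrated to a true 2.5% upper tail they were 86.5% vs 85.5% and 87.7% vs 88.6%, against 83-84% unadjusted. **This stands:** most of the gain recovers the conservatism of CMH, and even at R² = 0 the adjusted test shows +1.6 points. But the plan specifies CMH at its nominal level, so it would not collect that gain.

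A reader might infer that the plan forfeits a fixed 4-5 points of power and also keeps material confounding. The documents do not support this. They give no R² or c-statistic, and 4-5 points needs an R² of about 0.08-0.10. Nor do the two losses coincide: that gain arises with balanced groups, where there is no systematic confounding to leave behind, while the residual bias was largest under prognosis-aligned imbalance, where the gain shrank or vanished. The bias is also small against a 20-point effect.

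A reader might also infer that the trial falls short of 80% power. That is not shown either: with balanced groups CMH sat at about 80% with 400 controls and 82-83% with 600. What fails is the reason 10.1 gives.

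**Conclusion.** The point holds in limited form and is worth acting on. The ten factors enter only the propensity model. The CMH test built on it is conservative (about 3.6-4.6% at nominal 5%), and it showed no power gain over an unadjusted test with balanced groups. The step in 10.1 from 79% to at least 80% is therefore unsupported.

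For an assumed R² of about 0.03-0.16, modelling LPFS on the factors gains roughly 2-6 points of power with balanced groups, and between about −1 and +5 under imbalance, depending on its direction. Residual bias of about 0.3-1 percentage point falls to about 0.1-0.25. These sizes depend on assumed covariate frequencies and effects. Unmeasured differences from controls treated between 2001 and 2016 are untouched by either analysis.

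**What to change.** - Pre-specify as the confirmatory analysis a logistic model of 6-month LPFS with treatment group, propensity stratum and the ten factors, tested by the score test for group.
- Report the risk difference standardised to the phase 2 patients (predicted control LPFS for each), with a bootstrap interval.
- Keep the stratified CMH test as supportive.
- In 10.1, derive power for the chosen analysis over a stated range of R² (0 to 0.20 would do), or withdraw the claim that adjustment lifts it to at least 80%. In the same edit, name the test behind 79% (86%), reconcile 400 with more than 600 controls, and point the cross-reference to section 9 instead of section 8.

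The cost is SAP wording and a little programming; no new data are needed. There are two downsides. The result depends somewhat on the outcome model: about 15-19 coefficients against roughly 137-200 failures, about 5 of them in the 5x5 Gy group, and fewer if many patients are not assessable at 6 months. Two-sided error may also run slightly above 5% (up to about 5.7%, with one simulated cell at 6.1% when strata were added), so check it by simulation before the model is fixed.

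### Section 9 states no overlap rule, so controls scoring below every phase 2 patient stay in an open-ended lowest stratum and can leave a small residual bias

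*Combined protocol and SAP*

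**What the plan says.** Section 9 (Comparisons to Historical Control Group) sets out the comparison as follows.

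- **Score:** "a non-parsimonious multivariable logistic regression model will be estimated", using the ten listed prognostic factors, all grouped.
- **Controls:** "patients fulfilling the same inclusion criteria and exclusion criteria as defined in the prospective phase II study are considered". They must also have received at least 80% of the planned dose. More than 600 are expected; section 10.1 assumes about 400.
- **Strata:** because the two data sets differ so much in size, "the stratum boundaries will be based on the values of the propensity score for the phase II data alone". The number of strata is worded loosely: "One approach is to use quintiles of the estimated propensity scores to determine the cut-offs for the different strata". The balance model then uses "propensity score quintile (codes as a class variable with 4 degrees of freedom", which means five strata.
- **Estimate and test:** adjustment consists of "calculating the treatment effect within strata and then pooling the strata-specific treatment effect estimates", with no weights given. The test is described so: "to compare binary study endpoints after stratification of patients by propensity scores Cochran-Mantel-Haenszel tests were performed".
- **Check:** F-statistics for treatment arm before and after adjustment are compared "to determine whether balance was achieved after stratification based on the propensity score", and calibration is examined within quintiles. No threshold or consequence is attached.

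No section states a common-support rule, a trimming rule or a lower limit for the lowest stratum.

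**The concern.** Quintile cut-offs give four inner boundaries and no outer ones. Everything below the phase 2 patients' 20th percentile goes into the lowest stratum, including controls whose score is lower than that of any phase 2 patient. With 40 evaluable patients, that stratum holds about 40/5 = 8 of them. The highest stratum is open in the same way, but few controls are expected there.

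Within so wide a stratum the two groups may still differ on the ten factors. If those factors also predict local progression-free survival (LPFS), the stratum's effect estimate keeps part of the crude confounding and carries it into the pooled estimate. Section 10.1 makes this comparison the confirmatory aim. Leaving the rule open would also allow trimming to be decided after outcomes are known.

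**Working it through.** **The plan's own figure.** The documents give no share of controls per stratum and no bias figure. The nearest stated number is the power in section 10.1: 79% (86%) for 40 vs about 400 patients, 87% vs 67%, two-sided 5% (10%). Exact enumeration gives 80.7% (89.5%) for the Pearson test and 79.2% (86.5%) for Fisher's exact test, so the inputs reproduce it closely, with Fisher matching both. They set the scale: a target effect of 87 − 67 = 20 points.

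**Share of controls in the lowest stratum.** Assume normal scores with standardized difference d between groups. Then:

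- share below the phase 2 20th percentile = Φ(−0.842 + d)
- c-statistic = Φ(d/√2)
- share below the expected minimum of 40 phase 2 scores = Φ(−2.16 + d)

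| d (assumed) | c | In lowest stratum | Below the expected minimum |
|---|---|---|---|
| 0 | 0.50 | 20% | 1.5% |
| 0.50 | 0.64 | 37% | 4.8% |
| 0.84 | 0.72 | 50% | 9.3% |
| 1.50 | 0.86 | 75% | 25.5% |

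**Simulation with the plan's coding.** The ten factors give 8 (binary) + 4 (tumor type) + 2 (time developing motor deficits) = 14 slopes. Setup: 40 study patients vs 400 or 600 controls, fitted logistic score, cuts at the study patients' quintiles, no true effect, 600 runs per setting. Prevalences, shifts and prognostic strengths are assumptions; control LPFS averaged about 60%. Study patients were given the better prognosis. Trimming here drops controls below the lowest study score. Bias is in percentage points.

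| Assumed difference | c (fitted) | Controls in lowest stratum | Below every study patient | Crude bias | Pooled bias, all controls | Pooled bias, trimmed |
|---|---|---|---|---|---|---|
| none | 0.67 | 43% | 8% | 0 | 0.0 | 0.0–0.1 |
| small | 0.69 | 46–47% | 9% | 5 | 0.5 | 0.2 |
| moderate | 0.74 | 54–55% | 12–13% | 10 | 1.0 | 0.3–0.4 |
| larger | 0.80 | 64–65% | 19% | 14 | 1.6–1.7 | 0.5 |
| strong | 0.85 | 74% | 27–28% | 17 | 2.4–2.5 | 0.7 |

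Repeats with the same coding, other assumed shifts and trimming to the phase 2 range:

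- 1,200 runs, shifts of 0.2 to 0.5 SD: 0.8–2.5 points untrimmed and 0.3–0.9 trimmed. The SD of the estimate was 7.0–7.7 points either way.
- 800 runs: about 0.3–1.4 untrimmed and 0–0.9 trimmed, with 8–23% of controls outside the phase 2 range.

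**Why crowding alone does little.** Mantel-Haenszel weights are n₁n₀/(n₁+n₀). Take 600 controls with 43% (258) in the lowest stratum and the other 342 spread evenly, 85.5 per stratum:

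- lowest stratum: 8×258/266 = 7.76
- each other stratum: 8×85.5/93.5 = 7.32
- weight of the lowest stratum: 7.76/(7.76 + 4×7.32) = 21%

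The simulated weight was 21–27%.

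**Where the residual bias sits.** With 400 controls, the lowest stratum's own bias is 2.9 points (moderate) and 8.2 points (strong). Its approximate contribution is 0.232×2.9 = 0.7 of the 1.0 point, and 0.273×8.2 = 2.2 of the 2.5 points. Trimming lowers that stratum's bias to 0.1 and 1.6 points.

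**Precision cost.** A crude bound uses √(1/40 + 1/n₀). Dropping 28% of 600 (to 432) raises it by a factor √(0.02731/0.02667) = 1.012. Dropping 28% of 400 (to 288) gives √(0.02847/0.02750) = 1.017.

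**The case against.** **Cutting on phase 2 scores is a recognized choice.** It guarantees study patients in every stratum and targets the effect in patients like them, and the plan gives a reason for it. This stands: the boundaries are sound, and only the overlap rule is missing.

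**A reader might infer that about half of the controls land in the lowest stratum and that this biases the result.** The documents support neither step. The separation is unknown and the share could be about 20–75%. It is 43% with no group difference and no bias, because 14 slopes are fitted to 40 study patients. Controls below every study patient are 8–28% of all controls, a minority of that stratum.

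**A reader might infer a bias in favour of 5x5 Gy.** No section says which group has the better prognosis. The sign follows the crude confounding and could run against 5x5 Gy.

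**A reader might attach much larger figures to the open stratum.** Simulations in which grouping the covariates discards prognostic information give biases of 2.4/3.9/4.7/5.8 points. After trimming, 2.0/3.2/3.8/4.5 remain, which is 83%, 82%, 81% and 78%. Those biases, and the raised false-positive rates that go with them, mainly reflect dichotomisation, a separate matter.

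**The balance and calibration checks could reveal the problem.** They could, but nothing follows from them. The synopsis and section 10.1 speak of a matched control group, yet section 9 specifies only stratification, with no matching rule that would remove distant controls.

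**Range trimming is one option among several and rests on the extremes of about 40 overfitted scores.** This is fair: one extreme study patient can set the limit. A simple prespecified rule is still better than none.

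**Conclusion.** The gap is in the text. The outer strata are open-ended and controls unlike any phase 2 patient are kept. The consequence is conditional and small: about 0.3 to 2.5 points of residual bias when the groups differ on prognostic factors, 0 to 0.9 after trimming, and none when they do not differ. At the upper end this is 2.5/20 = 12.5% of the target effect and about a third of the SD of roughly 7 points. It is far below the crude bias in the same simulations (5 to 17 points).

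These sizes rest on assumed prevalences, shifts and prognostic strengths, on five strata, and on Mantel-Haenszel-type weights, which the plan does not state. Controls date from 2001 to 2016, so real differences are plausible, but their size and direction are unknown. This is a cheap improvement and does not overturn the planned comparison.

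**What to change.** Add one sentence to section 9:

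> Controls with a propensity score outside the range observed in phase 2 patients are excluded before stratification; the number excluded is reported.

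The phase 2 boundaries can stay. The sentence should be fixed before outcomes are compared.

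Cost: no new data or patients, and no effect on treatment. In simulation roughly 8–28% of controls are dropped, which is 48 to 168 of 600 or 32 to 112 of 400. The loss of precision is negligible, because the 40 phase 2 patients drive the variance.
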